17.11 CMR Protocol

A cardiac magnetic imaging (CMR) examination will be obtained in approximately 150 patients at selected sites although will not be selected on the basis of any specific criteria of their COVID-19 disease. Patients will be asked for consent to participate in this additional assessment at the time of their consent to participate in the study. The CMR study will be performed at the time of the 28-day visit; if this is not possible, the procedure will be arranged for the Day 45 visit. It is anticipated that all such patients will have been discharged from hospital by this time and will be asked to return as outpatients for the procedure.

CMR is well established as an excellent method to assess cardiac structure (including tissue characteristics) and function. It is the prime method to detect cardiac inflammation and is used extensively to diagnose and follow patients with inflammatory heart diseases, as well as the consequences – including, edema, necrosis, scar, regional and global dysfunction, chamber dilatation and heart failure. Importantly, CMR has now been established as a reproducible means to detect and quantitate fibrosis that results from the inflammation. CMR has become the standard for diagnosis of myocarditis in North America using established diagnostic criteria (Lake Louise Criteria for CMR in myocardial Inflammation (1); these criteria have more recently been updated (2).

RATIONALE

There are two rationales for adding CMR to this study:

1. There have been limited reports of CMR findings in patients with COVID-19. In one small study of recovered patients, Huang and colleagues (3) reported that 58% of the patients had abnormalities on CMR, consisting of edema and scarring, with the latter reflected by late gadolinium enhancement. In a more recent report (4) that has received extensive attention, 100 patients who had recovered from COVID-19, had a CMR examination. Two thirds of these patients had mild disease and had recovered at home. However, 33 of the 100 patients had more severe disease and were treated in hospital; 28 received supplemental oxygen and 2 required mechanical ventilation. The time from the onset of illness to the CMR examination ranged from 64 - 92 days. At the time of the CMR, 5 patients had significantly elevated hs-troponin suggestive of ongoing myocyte destruction, whereas another 71 patients had detectable levels of hs-troponin.

A total of 78 of these patients had abnormal CMR examinations. There was raised myocardial native T1 values (suggestive of edema or scar) in 73 patients and raised myocardial native T2 values in 60 (consistent with inflammation). In addition, approximately one third had myocardial late gadolinium enhancement and 22 had pericardial enhancement. On the day of the examination, some patients had persistent symptoms; atypical chest pain in 17, palpitations in 20, and slightly more than a third complained of ongoing shortness of breath and general exhaustion. Of these patients, 25 had symptoms with less than normal activity, although only 4 had been treated in hospital. This reported prevalence of symptoms and abnormal CMR findings is higher than that in other, albeit, smaller studies. Clearly, there is a need for further investigation to help clarify the extent and nature of ongoing cardiac inflammation in these patients.

2. Importantly, the proposed study will allow us to actually quantify the amount of fibrosis (by measuring the cardiac extracellular volume) in these patients and to compare the active treatment group to those treated with placebo. It would be an important observation if the patients treated with CardiolRx have less fibrosis than the placebo-treated group, offering convincing collaboration of our pre-clinical findings in which CBD significantly reduced myocardial fibrosis in the presence of inflammation.

STATISTICAL ANALYSIS

There will not be a baseline CMR study for comparison. Therefore, the mean values of the parameters of interest (see below) will be compared between the active and the placebo groups after 28 days of treatment with CardiolRx. An added benefit will be the opportunity to compare ultrasound measures of structure and function with the CMR variables in the same patients, and on the same day.

CMR ANALYSES

- Analyses will be performed in a core laboratory using the standardized operating procedures of the CMR Core Lab.

SOFTWARE AND DATA FORMAT

- cvi42 version 5.11 (Circle CV Imaging Inc., Calgary, AB, Canada) will be used for CMR analyses. This software is FDA (CFR 21 part 11) approved, and the software respects all Core lab requirements for the CMR analysis.
- Evaluation contours and quantitative results will be transferred in the format <cvi42 workspace> or as CSV data, respectively.

CMR IMAGE QUALITY ASSESSMENT

Before the evaluation, the submitted scan data will be assessed for completeness (all required images are available and can be evaluated) As well as for image quality. The image quality will be deemed adequate, if the following criteria are fulfilled:

- The cardiac anatomical structures are clearly identifiable.
- The images and the regions of interest (especially the myocardium) are not significantly distorted by field inhomogeneities, motion artifacts, or other artifacts.
- A *Form of Acceptability* will be developed by the core lab in the (RedCap™) MUHC database and will be sent to the site for confirmation that the patient is accepted or refused in the study.

CMR: DIAGNOSTIC TARGETS AND PARAMETERS

1. LV/RV volume
 - LVEDVI, LVESVI
 - RVEDVI, RVESVI
2. LV/RV function
 - LVEF, RVEF
 - Strain: Global longitudinal strain (GLS), segmental GLS (segments 1-12)
 - LV-Cl
3. LV mass
 - LV mass index (g/m height), LV mass index (g/m² BSA)
4. LV edema
 - Global LV myocardial T1
 - Global LV myocardial T2
 - Segmental myocardial T1 (segments 1-12)
 - Segmental myocardial T2 (segments 1-12)
5. LV inflammatory injury
 - Global LV myocardial T1
 - Segmental myocardial T1 (segments 1-12)
 - Global Extracellular Volume (ECV)
 - Regional (>2SD above normal) Extracellular Volume (ECV)

PROPRIETARY AND CONFIDENTIAL

- Presence of necrosis/scar in LGE images [categorical value]

INCIDENTAL FINDINGS

Images will not be assessed for incidental findings. If the reader identifies a clinically significant abnormality beyond the scope of the trial, it will be reported to the Data Safety Monitoring Committee of the trial.

DATA TRANSFER AND STORAGE

1. Images will be transferred via a secured internet transfer protocol. The images will use a Core LAB anonymization tool. This tool will be used in a web browser.
2. The software will anonymize the patient data at the sender hospital and will send the de-identified to the CORE lab. The technical Director of the CMR Core lab will create the Anonymization tool to meet the requirements of the protocol.
3. The transfer will occur via a https secure protocol. The site will have one login and password to be able to use the tool. Once the Images are received at the CORE laboratory, the images will be assessed for acceptability and subsequent analysis.

REFERENCES

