4.1.5 Other Efficacy Parameters

Other efficacy parameters include the following:

- Percentage of patients developing any one of the primary endpoint components within 60 days post randomization
- CV mortality at 28 days post randomization
- Percentage of patients requiring dialysis within 28 days post randomization
- Win ratio of the Ordinal Outcome Scale endpoint within 60 days of randomization
- PICQ at Day 28 and at Day 60
- Development of severe lymphopenia, defined as < 1000 cells/ microliter within 28 days post randomization
- Change in (elevation of) hs-troponin, NT-proBNP, D-dimer and in inflammatory markers (hs-CRP, ferritin, TNF-alpha, IL-1 beta, IL-6, IL-10) from baseline to Day 7 (AUC)
- Change from baseline to peak elevation of NT-proBNP, D-dimer and in inflammatory markers (hs-CRP, ferritin, IL-1 beta, IL-6, IL-10) during the 28-day treatment period
- Change from baseline to peak elevation of LDH during the 28-day treatment period
- Difference in CMR parameters: LVEF, LVEDV, LVESV, LAESV, ECV, GLS, LV mass, LGE extent and edema between the two treatment groups after 4 weeks of study treatment (in a subset of patients at selected sites).

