8 INVESTIGATIONAL PRODUCTS, DOSE AND DURATION OF TREATMENT

8.1 *Investigational Product*

CardiolRx™ is pharmaceutically produced. It contains cannabidiol in a concentration of 100 mg/ml and is free of tetrahydrocannabinol (THC; <5 ppm).

8.2 *Administration, Dosage and Duration of Treatment*

Study drug will be administered orally (via syringe)* with food according to the following treatment schedule:

Study Day	a.m. dose [mg/kg of body weight]	p.m. dose [mg/kg of body weight]
	CardiolRx™ or placebo	CardiolRx™ or placebo
1	N/A	2.5
2	2.5	2.5
3	2.5	5
4	5	5
5	5	7.5
6 - 28	7.5	7.5

At each study visit, drug accountability will be done. New bottles of study medication will be dispensed at each study visit (Days 3, 5, 7, 14 and 21).

If the next higher dose is not tolerated, the patient should return to the last tolerated dose. The highest tolerated dose will be administered until Day 28 (4 weeks post randomization).

The maximum treatment period will be 28 days.

* If the patient requires mechanical ventilation, the study medication is administered through a naso-gastric tube.

Justification for Dosing Regimen

COVID-19 is an acute illness with, at times, rapid progression of symptoms and signs. Because of this, it seems important to increase the blood level of the investigational agent as quickly as possible to achieve the potential anti-inflammatory and anti-cytokine actions that are likely to be important in this population. However, this agent has not been administered previously to this population, so care must be taken to observe closely for

adverse drug effects or drug-drug interactions that might have significant negative consequences. A similar product containing a highly purified botanical extract of CBD has been approved for use in pediatric epilepsy to a dose up to 10 mg/kg twice daily (Devinsky et al. 2016). We have chosen to restrict the maximum dose in this COVID-19 population to 7.5 mg/kg b.i.d. because of the expected elderly and perhaps frail condition of some of the enrolled patients. Investigators are encouraged to decrease the dose if there are indications of intolerance of a given dose to the previously tolerated dose.

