9.2.4 LVEF assessment by Echocardiography

The patient's LVEF will be assessed at baseline and at Day 28.

Each study will include 2-D echo images obtained from the standard parasternal and apical windows, with care taken to ensure on-axis views from all acoustic windows. LVEF will be calculated by standard techniques. LV cavity dimensions in systole and diastole will be measured, as well as thickness of the interventricular septum and posterior wall according to current guidelines. LV mass and mass index normalized for body surface area will be calculated using standard formulae (Otterstad et al. 1997).

Biplane Simpson's method (Devereux et al. 1986) will be used for measurement of LV end-diastolic (LVEDV) and end-systolic (LVESV) volumes. Volume measurements obtained by this method have been shown to be both accurate and reproducible, with variation in the range of -5% to +5%. It is anticipated that the image quality will be adequate for accurate endocardial tracing in > 90% of patients.

LVEDV, LVESV, and LVEF will be calculated and averaged over 5 cardiac cycles, 10 cardiac cycles in patients with atrial fibrillation.

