9.2.13 Cardiac magnetic resonance imaging (CMR)

A subset of patients at selected sites will undergo a CMR at Day 28. The standardized examination protocol (Appendix 17.11) will include LVEF, LVEDV, LVESV, LAESV, ECV, GLS, LV mass, LGE extent and edema. All images will be analyzed at a Central CMR Core Laboratory.

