#### 4.1.5 Other Efficacy Parameters

Other efficacy parameters include:

- Percentage of patients developing any one of the primary endpoint components within 60 days post randomization
- CV mortality at 28 days post randomization
- Percentage of patients requiring dialysis within 28 days post randomization
- Win ratio of the Ordinal Outcome Scale endpoint within 60 days of randomization
- Patient Impression of Change Questionnaire (PICQ) at Day 28 and at Day 60
- Development of severe lymphopenia, defined as < 1000 cells/ microliter within 28 days post randomization
- Change in (elevation of) hs-troponin, NT-proBNP, D-dimer and in inflammatory markers (hs-CRP, ferritin, TNF-alpha, IL-1 beta, IL-6, IL-10) from baseline to Day 7 (AUC)
- Change from baseline to peak elevation of NT-proBNP, D-dimer and in inflammatory markers (hs-CRP, ferritin, IL-1 beta, IL-6, IL-10) during the 28-day treatment period
- Change from baseline to peak elevation of LDH during the 28-day treatment period
- Difference in cardiac magnetic resonance imaging (CMR) parameters: LVEF, LVEDV, LVESV, LAESV, ECV, GLS, LV mass, LGE extent and edema between the

---

two treatment groups after 4 weeks of study treatment (in a subset of patients at selected sites).

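### CMR means are to be compared without baseline adjustment although baseline echo supplies a covariate for four of the nine CMR measures, and Day 45 scans are accepted for a 4-week endpoint with no rule for handling them

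*Protocol*

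**What the plan says.** **Endpoint.** Protocol 4.1.5 names nine CMR parameters among the other efficacy parameters: "LVEF, LVEDV, LVESV, LAESV, ECV, GLS, LV mass, LGE extent and edema". Only some patients, at chosen sites, are scanned, and the contrast of interest is the one "between the two treatment groups after 4 weeks of study treatment". SAP 4.1.5 repeats this.

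**Timing.** Protocol 9.2.13 gives one time point: "A subset of patients at selected sites will undergo a CMR at Day 28". The Synopsis, Sections 6.3 and 9.1, the schedule in 17.2.1 (footnote 7) and Appendix 17.11 also allow Day 45. The appendix wording for a scan that cannot be done at Day 28 is "if this is not possible, the procedure will be arranged for the Day 45 visit". On dosing, Protocol 8.2 states: "The maximum treatment period will be 28 days".

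**Analysis.** Appendix 17.11 says "There will not be a baseline CMR study for comparison" and concludes that mean values will be compared between arms after 28 days of treatment. It names no covariate and says nothing about Day 45 scans. It also expects echo and CMR to be compared in the same patients on the same day.

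**Echo.** Protocol 9.2.4 says "LVEF will be assessed at baseline and at Day 28". The same section has LVEDV, LVESV and LV mass calculated from the images.

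**Status.** Protocol 10.1.3 treats the other endpoints as supportive. SAP 6.2 and 6.4 confine testing after early termination to the bio- and inflammatory markers, and SAP Section 9 contains no CMR analysis.

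**The concern.** There are two separate weaknesses.

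The first is a step in reasoning. Appendix 17.11 goes from the absence of a baseline CMR to an unadjusted comparison of means. That does not follow. A covariate need not come from the same imaging method; it has to precede randomization and predict the outcome. Baseline echo meets the first condition by design, and for the four shared measures it can be expected to meet the second. Protocol 11.2.2 and 11.2.3 already use ANCOVA for other continuous outcomes. At stake is precision in a subset of about 150 patients for which no effect size or power is stated.

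The second is the time point. A patient scanned at Day 45 is off drug and 17 days further into recovery, but would be reported under a label that describes the end of 4 weeks of treatment. With no handling rule, the analyst chooses after the fact whether to pool, separate or drop those scans. No echo is scheduled at Day 45, so those patients also miss the planned same-day comparison of the two methods.

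**Working it through.** The documents give no sample size, SD or power for CMR, so there is no CMR figure to reproduce. The 211 per group in Protocol 11.1 concerns the primary endpoint and does not depend on this point.

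**1. Which measures have a baseline echo value**

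- CMR list (Protocol 4.1.5): nine parameters.
- Echo list (Protocol 9.2.4): LVEF, LVEDV, LVESV, LV mass.
- Overlap: 4 of 9. No echo value is planned for LAESV, ECV, GLS, LGE or edema. ECV is the measure through which Appendix 17.11 proposes to quantify fibrosis.

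**2. Gain from the covariate (those four measures only)**

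Inputs: about 150 scans (Appendix 17.11), taken as 75 per arm (assumption: 1:1 holds in the subset). The correlation r between baseline echo and follow-up CMR is not given; 0.4 to 0.7 is assumed. For illustration, the LVEF SD is assumed to be 10 points.

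- Unadjusted SE = 10 × √(2/75) = 1.63 points.
- Adjusted SE = 1.63 × √(1 − r²): 1.50 at r = 0.4 and 1.17 at r = 0.7.
- Reduction = 1 − √(1 − r²): 8% and 29%. This does not depend on the assumed SD.
- Equivalent unadjusted sample = 150/(1 − r²): 179 and 294 patients.
- Detectable difference at 80% power, two-sided 0.05: (1.960 + 0.842) × √(2/75) = 0.457 SD unadjusted; × √(1 − r²) gives 0.419 SD at r = 0.4 and 0.327 SD at r = 0.7.

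**3. How far off drug a Day 45 scan is**

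- Gap: 45 − 28 = 17 days. The ±2-day window after Day 7 (Protocol 9.1) makes it 43 − 28 = 15 to 47 − 28 = 19 days.
- Half-life: Protocol 9.2.14.2 equates 6 half-lives with 18 days, so 18/6 = 3 days.
- Drug remaining = 0.5^(gap/3): 3.1% at 15 days, 2.0% at 17, 1.2% at 19.

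**4. What late scans could do (all inputs assumed)**

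- Unequal shares: if 15% of active and 30% of placebo scans are late and the parameter improves by d between the two days, the pooled difference shifts by (0.30 − 0.15) × d = 0.15d toward no effect. With equal shares the shift is zero.
- Fading effect: take a true on-drug effect of 0.457 SD, late share f in both arms, and fraction k of the effect remaining. The pooled effect is 0.457 × (1 − f(1 − k)). Power starts at 80%:

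| Late share f | k = 1 | k = 0.5 | k = 0 |
|---|---|---|---|
| 10% | 80% | 76% | 71% |
| 20% | 80% | 71% | 61% |
| 30% | 80% | 66% | 50% |

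**5. Would a Day 28-only main analysis be better?**

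- In the 15%/30% scenario it drops 0.15 × 75 + 0.30 × 75 = 33.75, about 34 of 150 scans (22%).
- SE = 10 × √(1/63.75 + 1/52.5) = 1.86. With the covariate at r = 0.4 it is 1.86 × √0.84 = 1.71, still worse than 1.63 for all scans unadjusted.
- Scan day is settled after randomization, so the restriction also selects patients on a post-randomization event.

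**The case against.** The best defence is that little depends on this. CMR is a supportive endpoint in a subset, and the SAP, written after early termination, plans no CMR test. The planned 75 per arm may never have been reached. Appendix 17.11 names no test and does not forbid covariates. Randomization stratified by center means that an unadjusted comparison is valid: chance imbalance is already in its standard error, so adjustment improves efficiency and corrects no error. Protocol 9.2.4 expects adequate images in more than 90% of patients, not in all. All of this stands and limits the severity.

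Three stronger readings are tempting, and the documents do not support them.

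- A reader might infer that baseline echo covers the CMR endpoint generally. It covers four of nine measures and leaves out ECV.
- A reader might infer that sicker patients, and more of them on placebo, are scanned late, so that the result is biased toward no effect. The only stated trigger is that a Day 28 scan is not possible. No reason for delay and no share by arm is given, and Appendix 17.11 expects all these patients to have been discharged by then.
- A reader might infer that the 4-week label is false for Day 45 scans. A patient who completed dosing has had 4 weeks of treatment before either scan. The label is ambiguous as to whether the scan must be on treatment.

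The objection does not remove the two gaps themselves: a useful covariate left unused, and a second scan day with no handling rule.

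**Conclusion.** Both gaps are documented; their consequence is small. For LVEF, LVEDV, LVESV and LV mass, adjusting for baseline echo would reduce the standard error by about 8% to 29%, given 75 per arm and correlations of 0.4 to 0.7, neither of which the documents confirm. For the other five measures there is no such gain.

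The timing gap applies to all nine measures. Day 45 scans are effectively off drug, Protocol 9.2.13 disagrees with the sections that permit them, and their handling is undefined. Whether they bias or dilute the comparison depends on unequal late shares by arm or on the effect fading after dosing ends. The documents establish neither, so the bias and power figures above are illustrations, not estimates.

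It may also seem to follow that the main analysis should be restricted to Day 28. It should not: that would condition on a post-randomization event and, in the scenario used here, cost more precision than the covariate recovers at r = 0.4. Severity is low.

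**What to change.** 1. In Appendix 17.11, and in the SAP if any CMR comparison is reported, compare LVEF, LVEDV, LVESV and LV mass by ANCOVA with the baseline echo value of the same measure as covariate. Use echo as a covariate and do not subtract it from the CMR value, since the two methods differ. State in advance how patients without a usable baseline echo are kept in the analysis.
2. Reconcile Protocol 4.1.5, 9.2.13 and Appendix 17.11 with SAP 4.1.5, so that the endpoint definition covers both scan days and says that Day 45 scans are made after treatment has ended.
3. Keep every randomized patient's scan in the main comparison. Report the number of Day 28 and Day 45 scans per arm, and add a sensitivity analysis limited to Day 28 scans (±2 days).
4. Limit the same-day comparison of echo and CMR to patients with a Day 28 scan.

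The cost is a few lines of text and no new data. If the SAP stays descriptive after early termination, item 1 belongs in Appendix 17.11 only; for any CMR summary, the correct time label and the scan-day counts by arm are still needed.

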## 1 LIST OF ABBREVIATIONS

Abbreviation	Definition
AE	Adverse Event
ACE	Angiotensin Converting Enzyme
ALT	Alanine aminotransferase
AMI	Acute myocardial infarction
ARB	Angiotensin Receptor Blocker
AST	Aspartate aminotransferase
ATC	Anatomic Therapeutic Chemical
AUC	Area under the curve
BNP	Brain natriuretic peptide
CEC	Clinical Endpoint Adjudication committee
CMR	Cardiac magnetic resonance imaging
CRF	Case Report Form
C-SSRS	Columbia-Suicide Severity Rating Scale
CV	Cardiovascular
ECMO	Extracorporeal Membrane Oxygenation
eCRF	Electronic Case Report Form
ECG	Electrocardiogram
ECV	Extracellular volume
eGFR	Estimated Glomerular filtration rate
HF	Heart failure
hs-CRP	High sensitivity-C-reactive protein
hs-troponin	High sensitivity-troponin
ICU	Intensive Care Unit
INR	International normalized ratio
ITT	Intention-to-treat
LDH	Lactate dehydrogenase
LGE	Late gadolinium enhancement
LV	Left ventricular
LVEDV	Left ventricular end-diastolic volume

Abbreviation	Definition
LVEF	Left ventricular ejection fraction
LVESV	Left ventricular end-systolic volume
MedDRA	Medical Dictionary for Regulatory Activities
NT-proBNP	N-terminal pro b-type natriuretic peptide
PICQ	Patient impression of change questionnaire
PPP	Per protocol population
PT	Preferred Term
Q1 / Q3	First / third quartile
SAE	Serious Adverse Event
SAF	Safety Population
SAP	Statistical Analysis Plan
SD	Standard deviation
SD1	First study day
SOC	System Organ Class
TEAE	Treatment-emergent Adverse Event
TNF	Tumor necrosis factor
WHO	World Health Organization

## 2 INTRODUCTION

This document describes the Statistical Analysis Plan (SAP) for the CARDIOL 100-03 Protocol (Study to evaluate the Efficacy and Safety of CardiolRx™ in Patients with COVID-19 and Cardiovascular Disease or Risk Factors [LANCER]. This is a multi-center, double-blind, randomized, placebo-controlled, parallel group design, 1:1 randomization study. In total 422 patients will be randomized (1:1) to either CardiolRx™ or placebo.

The design and methods of the CARDIOL 100-03 study are described in detail in the study protocol Amendment 3, dated September 23, 2021. The criteria for evaluation of study results and the analysis populations are defined in section 10 of the study protocol and an outline of the statistical analysis plan may be found in section 11 of the same document. The purpose of this document is to describe the analyses that will be performed in accordance with the protocol in more detail.

As the study was terminated early an abbreviated set of reporting will be generated as described herein. This plan will be approved prior to the breaking of the study blind. Changes from the protocol are noted.

